6.8 CONCOMITANT MEDICATIONS/RESCUE MEDICATIONS

Subjects may continue their baseline medication(s) as long as the medications are not among the prohibited medications listed in Section 5.2.2. The daily dose of each medication should be maintained throughout the study since any changes to this background regimen may have an effect on the assessment. Subjects are allowed to increase dosage of NSAIDs or use analgesics to treat minor pain throughout the study, provided all concomitant medications are back to baseline dosages within 24 hours of a clinical assessment visit.

If for any reason deemed necessary by the investigator, such as in the event of a substantial disease flare which cannot be treated with increased drugs (NSAIDs) or narcotic, a rescue medication can be initiated at any time that is in the best interests of the subject. Rescue medication should be carefully considered by the principal investigator (PI) since there may be an effect on the results of the study. All changes and start and stop dates, and the indication for which it was given must be recorded in the source documents and eCRF. Routine changes (dose, route, etc.) to the background treatments should not be performed.

6.9 STOPPING CRITERIA

6.9.1 Criteria for Adverse Event Assessment

All AEs will be graded according to the RCTC v.2.0 (Appendix B). Please refer to Section 8.0, Safety Assessments for additional information.

6.9.2 General Criteria for Stopping Study Drug

The study drug will be permanently discontinued for any subject who meets a DLT criterion as outlined in Section 3.2.

6.9.3 Stopping Criteria

Any \geq Grade 3 event considered related to the study drug and occurring during administration of the study drug will result in its permanent discontinuation for that subject. The Medical Monitor should be notified immediately and the subject should be followed for safety as clinically indicated until the toxicity resolves and in the opinion of the investigator, no further follow-up regarding the toxicity is needed.

6.10 WITHDRAWAL OF SUBJECTS FROM STUDY

Subjects will be free to withdraw from treatment or from the study at any time for any reason, or they may be withdrawn/removed, if necessary (see reasons for withdrawal below). It is understood by all concerned that an excessive rate of withdrawals can render the study uninterpretable; therefore, unnecessary withdrawal of subjects should be avoided.

Subjects will be removed from treatment for the following reasons:

- Unacceptable acute toxicities defined as:
 - Occurrence of a DLT

Subjects will be removed from the study for the following reasons:

- Withdrawal of consent
- Non-compliance/Lost to follow-up
- Pregnancy

If treatment with study drug is interrupted and permanently stopped, subjects should remain on study and will be followed for scheduled safety and study assessments through Day 35. If the subject goes onto other treatment, this should be noted in the source documents and the concomitant medications eCRF.

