5.2.2 Prohibited Medications

Subjects should not receive any of the following medications through Day 94 and for the additional times specified below:

- Topical, oral or injectable steroids for 1 month prior to screening, or intra-articular-visco-supplementation within 3 months prior to screening;
- Any capsaicin-containing product on or in the vicinity of the knee within 4 weeks prior to screening;
- Topically applied products (including emollients or moisturizers) on or in the vicinity of the knees within 2 days prior to the first application of study drug;
- Topical or any other therapy on the knees that, in the Investigator's opinion, might affect the study evaluation of signs/symptoms;
- Daytime use of medications or substances (alcohol, benzodiazepines, barbiturates, muscle relaxants, tranquilizers, hypnotics) that could diminish cognitive ability to comply with study procedures;
- Investigational drug, device or therapy within 30 days prior to screening.

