6.7 RECOMMENDATIONS FOR MANAGEMENT OF POTENTIAL TOXICITIES

6.7.1 Allergic Reaction, Burning, or Pruritus

In the case of any life-threatening event occurring during the treatment, the study drug must be immediately and permanently discontinued. While corticosteroids are strongly discouraged, they may be used if they are necessary for the safety of the subject.

• Rash/pruritus/urticaria

- If subject develops rash, pruritus, or urticaria, interrupt treatment if it is ongoing and promptly assess subject for any other associated signs/symptoms (e.g., hypotension, fever, respiratory distress).
 - Consider treating with H2 receptor antagonists as clinically indicated.
 If rash / pruritus / urticaria is isolated and resolves either spontaneously or with intervention, treatment with the study drug may be restarted.

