9.5.2 Treatment Administration/Compliance

The Investigators will be responsible for the storage, dispensing, inventory, and accountability of all clinical supplies. An accurate, timely record of the disposition of all clinical supplies must be maintained. Subjects may be withdrawn from the study by the Sponsor for non-compliance with the protocol.

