9.5.7 Interim Analyses

Interim analyses will be performed at Days 19, 35, and 64 per 9.5.3 and 9.5.3.1 above,

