6.3 Clinical Response

Clinical response will be measured by reduction of WOMAC pain score on the Study Knee. In order for a subject to be considered to have successfully obtained a clinical response, the following criteria must be met: WOMAC pain score on the Study Knee reduced to 50% or less of baseline at any of the stated assessment times.

A subject with a missing WOMAC pain score on the Study Knee at a visit will be considered to have failed to achieve a clinical response for that visit.

The durability of clinical response up to Day 94 will be evaluated by a tabulation of clinical response at Days 19, 35, 64, and the Day 94 visit by treatment group. Subjects who have successfully met the above criteria (reduction of a least 50% in WOMAC pain score) at the Day 5 visit and who remain at least at this reduction of pain score or lower at the Days 19, 35, 64, and the Day 94 visit will be considered to have a durable clinical response through Day 94. Subjects who at no more than one of the post Day 5 visits have less than 50% reduction in WOMAC pain score will be considered to have a durable response through the last day at which reduction in WOMAC pain score is at least 50%. Patients who have less than 50% WOMAC pain score reduction on two or more of the post Day 5 visits will be considered to have failed to achieve a durable clinical response.

Each subject's clinical response status (Responder vs. Non-responder) at each visit and the durability of clinical response up to Day 94 will be summarized for each treatment group. Percent change from baseline in WOMAC pain score on both knees will be listed at each visit.

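### Removing subjects from the study for non-compliance or pregnancy after Day 4 stops no treatment; it only ends outcome collection, and if non-compliance differs by arm it can bias the Day 35 comparison

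*Protocol*

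**What the plan says.** Protocol 6.10 has two lists. Removal from treatment has one reason, a dose-limiting toxicity. The second list begins "Subjects will be removed from the study for the following reasons" and includes "Non-compliance/Lost to follow-up" as one item and pregnancy as another. SAP 3.2.4 repeats both lists. Neither document defines non-compliance or says when the rule stops applying.

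The wording is not uniform. The opening of 6.10 says of subjects that "they may be withdrawn/removed, if necessary" and asks sites to avoid unnecessary withdrawal. Protocol 9.5.2 says "Subjects may be withdrawn from the study by the Sponsor for non-compliance with the protocol". Section 6.10 also keeps subjects who permanently stop study drug under scheduled assessment, but only through Day 35.

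Dosing is on Days 1 to 4 and follow-up runs to Day 94 (Protocol 3.1). Protocol 9.5.8 and SAP 4.4 leave missing values missing, apart from single WOMAC items. For the responder analysis SAP 6.3 says: "A subject with a missing WOMAC pain score on the Study Knee at a visit will be considered to have failed".

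Three sections bear on what compliance means after Day 4. Protocol 5.2.2 says "Subjects should not receive any of the following medications through Day 94", and its list includes steroids. Protocol 6.7.1 says "While corticosteroids are strongly discouraged, they may be used if they are necessary for the safety of the subject". Protocol 6.8 allows temporary NSAID increases, analgesics and, at the investigator's judgement, rescue medication.

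**The concern.** Once the four applications are done there is no study treatment left to stop. Removing a subject on Day 20 therefore changes only what is recorded: the Day 35, 64 and 94 WOMAC and VAS scores, and the routine adverse-event and laboratory follow-up.

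Non-compliance could plausibly differ by arm. Uncontrolled knee pain might lead to disallowed therapy, more often in the less effective arm. Application-site discomfort might lead to missed applications, more often on active: in VZU00023 burning-stinging pain was reported by 100% of CGS-200-5 subjects and 35% of vehicle subjects (Protocol 1.3). If removed subjects also do worse than those who remain, the observed Day 35 mean in their arm is too favourable. A rule in the protocol would then be creating informative missing data in a trial that does not impute missing visits.

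**Working it through.** **1. The plan's own figure.** Inputs from SAP 9: n = 40 per arm, difference 63, SD 100, two-sided 5%. SE = 100 × √(2/40) = 22.36. 63/22.36 − 1.96 = 0.857, which gives power of 80.4% (79.5% with the noncentral t). The stated 80% reproduces.

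**2. What happens to a subject removed between Day 5 and Day 35.**
- Scores already collected stay in the database.
- An early-termination WOMAC and VAS are listed (Protocol 6.5 and Table 6–3), but 6.5 introduces its activities as discretionary.
- SAP 4.3 sets no analysis windows and uses the visit as recorded. No rule uses an early-termination score for Day 35.
- The primary ANCOVA (SAP 6.1) uses change at Day 35, so the subject does not contribute.
- In SAP 6.3 the subject is a non-responder at every missed visit.
- Protocol 4.2 may allow replacement (up to 10 per arm). This restores the number of subjects but not the lost outcomes.

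A subject removed after Day 35 still contributes the primary endpoint and loses only later visits.

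**3. Size of a possible bias.** The documents give no removal rate, so f and g are assumptions. Let f be the share of an arm removed, m the mean improvement of those retained, and g the number of points by which removed subjects improve less.
- Full-arm mean = (1 − f)m + f(m − g) = m − fg. The observed mean is too favourable by fg.
- With the same g in both arms, bias in favour of active = (f_active − f_vehicle) × g.
- 10% of one arm only, g = 60 to 100: 0.10 × 60 = 6 and 0.10 × 100 = 10 points. 6/63 = 10% and 10/63 = 16% of the target difference.
- 5% of one arm only, g = 50 to 150: 2.5 to 7.5 points, or 4 to 12% of 63.
- Equal f and equal g: 0.

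**4. Consequence by direction** (normal approximation, SD 100, no covariate adjustment, 36 subjects left in the affected arm and 40 in the other). SE = 100 × √(1/36 + 1/40) = 22.97.
- Vehicle affected, true difference 63, g = 60 to 100: expected observed difference 57 to 53. 57/22.97 − 1.96 = 0.52 and 53/22.97 − 1.96 = 0.35, so power is about 70% to 64%.
- Active affected, no true difference, g = 50 to 150 (bias 5 to 15 points): two-sided false-positive rate 5.5% to 10.0%, with 7.2% at g = 100.

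**5. Loss of numbers alone** (no bias, no replacement, equal arms): power 78.4% with 38 per arm, 76.2% with 36, 73.8% with 34 and 68.4% with 30.

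**6. Responder analysis.** Four removed of 40 is 4/40 = 10 percentage points of forced failure. That is the maximum effect, reached only if all four would otherwise have responded; it is zero if none would have.

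**The case against.** The strongest reply is that the text is softer than its list suggests. The opening of 6.10 and section 9.5.2 are permissive, and 6.10 discourages unnecessary withdrawal. The per-protocol set (SAP 4.2) and the sponsor's exclusions at analysis (Protocol 9.5.9) imply that subjects with deviations can stay on study. This stands in part: the documents do not settle whether removal is mandatory. It does not remove the problem, because the list itself uses mandatory wording in both documents.

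Several stronger readings are tempting and are not supported.
- *Prohibited therapy leads to removal.* No section says so. Protocol 6.8 gives a route for uncontrolled pain, although it does not say whether rescue may include a drug listed in 5.2.2.
- *A subject given a corticosteroid under 6.7.1 is thereby non-compliant.* Section 6.7.1 can be read as a specific safety exception to 5.2.2. The sections need reconciling; they do not prove the point.
- *Pregnancy removals depend on arm.* Nothing indicates this. Entry is at age 35 to 75, with negative pregnancy tests required before dosing where relevant, so cases should be few.
- *Data are discarded.* Collection stops; data already collected are kept. Unresolved serious events and pregnancies are followed to outcome (Protocol 8.1.4), and related serious events after the study are reported (8.1.5).
- *The sponsor could withdraw subjects in the light of interim results.* Protocol 9.5.7 says "Interim analyses will be performed at Days 19, 35, and 64 per 9.5.3 and 9.5.3.1 above", but neither document says who sees the results, so this is speculation.
- *The bias favours vehicle in the ANCOVA and penalises it by 10 points in the responder analysis.* The sign is unknown, since excess removal in an active arm reverses it, and 10 points is a ceiling because many such subjects would have failed anyway.

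**Conclusion.** The point holds as a wording defect with a real but unquantifiable consequence. Protocol 6.10 and SAP 3.2.4 do not separate stopping treatment from leaving the study for non-compliance, leave non-compliance undefined, set no end date, and conflict with the permissive wording in the opening of 6.10 and in 9.5.2. With no imputation of missed visits and no use of early-termination scores for Day 35, outcomes can be lost in a way related to arm.

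The shift of 6 to 10 points (10 to 16% of 63) rests on two assumptions: 10% removed in one arm and none in the other, and 60 to 100 points less improvement in those removed. At lower or balanced removal the effect is small or nil. The arm-dependence argument rests on non-compliance alone. This is a cheap improvement worth making; it does not show that the planned comparison is biased.

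**What to change.** - In Protocol 6.10, SAP 3.2.4 and Protocol 9.5.2, limit removal from the study to withdrawal of consent and loss to follow-up, and make the mandatory and permissive wording agree.
- For all other subjects, including those who are non-compliant, become pregnant or stop study drug, continue the already scheduled efficacy and safety assessments to Day 94. Reconcile this with the Day 35 limit in 6.10. The change concerns data collection only and sets no treatment rule.
- Define non-compliance and record it as a protocol deviation. SAP 5.2 already tabulates deviations, and the per-protocol set in SAP 4.2 already handles major ones.
- Reconcile Protocol 5.2.2, 6.7.1 and 6.8 on steroids and rescue medication, so that it is clear which use counts as a deviation.

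The cost is a wording amendment to the protocol and SAP and attendance at some already scheduled visits; no procedure is added. The small downside is that some retained scores will be observed under prohibited or rescue therapy. These can be identified from the concomitant-medication data, but they are not a record of the outcome without that therapy.

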3.0 STUDY DESIGN

3.1 OVERALL STUDY DESIGN

This is a multi-center, randomized, double-blind clinical trial to examine the comparative effects on OAKP of CGS-200-1 (1% Capsaicin content) (N=40), CGS-200-5 (5% Capsaicin content) (N=40), and CGS-200 Vehicle (no Capsaicin) (N=40) in subjects with OA of the knees according to the 1986 ACR criteria. Assigned doses will be applied at the clinic for 60 minutes on each of four consecutive days.

Subjects will be randomized to one of the three Arms in this study: CGS-200-1 or CGS-200-5 or CGS-200-0 (Vehicle). All subjects will receive 4 consecutive days of treatment and will then be followed up until the Day 94 visit.

Subjects will receive the study arm appropriate treatment as a topical application over the frontal aspect of the knee(s) once daily on four consecutive days. The applications will be at the clinic but by the subject wearing gloves under supervision of clinic personnel. The application will be left in place for 60 minutes and then washed off at the clinic by clinic personnel. The amount of Investigational Drug Product to be applied is estimated to be approximately 0.13 mL based on experience in prior studies. Even though both knee(s) will receive application of study test materials, with regard to reduction in WOMAC pain and VAS pain score associated with study treatments, only one knee will be indicated as the "Study Knee". This will be the knee with the highest WOMAC pain score at baseline. If both knees have equal WOMAC pain scores at baseline, then the right knee will be considered the "Study Knee" with regard to WOMAC pain and VAS pain score reduction.

Data will be collected from Day 1 through Day 5 and then again on Days 19, 35, 64, and 94 for efficacy, tolerability, and safety measures. The Investigators, all site staff and Clinical Research Organization (CRO) personnel (except the Medical Monitor providing safety oversight) directly involved in the study will remain blinded to the treatment assignment throughout the trial.

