8.1.4 Follow-up of Adverse Events

Adverse events will be captured from start of study drug treatment through Day 94. AEs are followed until final outcome is known or until the end of the study Day 94. AEs that are not resolved as of Day 94 are recorded on the AE eCRF as ongoing and in the outcome field as Not Recovered/Not Resolved.

SAEs that have not resolved by Day 94 are followed until final outcome is known. If it is not possible to obtain a final outcome for a SAE (e.g., the subject is lost to follow-up), the reason a final outcome could not be obtained will be documented by the investigator.

Pregnancy:

All reports of pregnancy, or partner pregnancy, occurring after treatment with study drug and up to Day 94 must be reported via the Pregnancy Report form to Safety as per Section 8.1.2. Pregnancy itself is not an AE or SAE. However, any events arising during the pregnancy will be assessed and reported accordingly as an AE or SAE. A spontaneous abortion is always considered to be an SAE and shall be reported on the SAE Worksheet. Furthermore, any SAE occurring as a result of a post-study pregnancy and considered reasonably related to the investigational product by the investigator will be reported to Safety. All reported pregnancy cases will be followed up until outcome.

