3. INVESTIGATIONAL PLAN

3.1 Study Design

This is a multi-center, randomized, double-blind clinical trial to examine the comparative effects on OAKP of CGS-200-1 (1% Capsaicin content) (N=40), CGS-200-5 (5% Capsaicin content) (N=40), and CGS-200 Vehicle (no Capsaicin) (N=40) in subjects with OA of the knees according to the 1986 American College of Rheumatology (ACR) criteria. Assigned doses will be applied at the clinic for 60 minutes on each of four consecutive days.

Subjects who meet the inclusion/exclusion criteria specified in the Protocol, Section 4.1 will be randomized to one of the three Arms in this study: CGS-200-1 or CGS-200-5 or CGS-200-0 (Vehicle) in a 1:1:1 ratio. All subjects will receive 4 consecutive days of treatment and will then be followed up until the Day 94 visit.

Even though both knee(s) will receive application of study test materials, with regard to reduction in WOMAC pain and VAS pain score associated with study treatments, only one knee will be indicated as the “Study Knee”. This will be the knee with the highest WOMAC pain score at baseline. If both knees have equal WOMAC pain scores at baseline, then the right knee will be considered the “Study Knee” with regard to WOMAC pain and Visual Analogue Scale (VAS) pain score reduction.

Data will be collected from Day 1 through Day 5 and then again on Days 19, 35, 64 and 94 for efficacy, tolerability, and safety measures. See Appendix C for the Schedule of Events.

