3.2.4 Subject Compliance

Subjects will be free to withdraw from treatment or from the study at any time for any reason, or they may be withdrawn/removed, if necessary (see reasons for withdrawal below). It is understood by all concerned that an excessive rate of withdrawals can render the study uninterpretable; therefore, unnecessary withdrawal of subjects should be avoided.

Subjects will be removed from treatment for the following reasons:

- Unacceptable acute toxicities defined as:
 - Occurrence of a Dose-limiting toxicity (DLT)

Subjects will be removed from the study for the following reasons:

- Withdrawal of consent
- Non-compliance/Lost to follow-up
- Pregnancy

If treatment with study drug is interrupted and permanently stopped, subjects should remain on study and will be followed for scheduled safety and study assessments through Day 35. If the subject goes onto other treatment, this should be noted in the source documents and the concomitant medications electronic case report form (eCRF).

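### Protocol 6.10 and SAP 3.2.4 schedule assessments to Day 35 for subjects who permanently stop study drug, against Day 94 for all subjects elsewhere, which creates avoidable missing data at Days 64 and 94

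*Protocol*

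**What the plan says.** Two follow-up periods are given for the same subjects.

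- **Day 35.** Protocol 6.10 says that after a permanent stop "subjects should remain on study and will be followed for scheduled safety and study assessments through Day 35". SAP 3.2.4 has the same rule: "followed for scheduled safety and study assessments through Day 35".
- **Day 94.** Protocol 3.1 states: "All subjects will receive 4 consecutive days of treatment and will then be followed up until the Day 94 visit". SAP 3.1 agrees that subjects "will then be followed up until the Day 94 visit". Neither makes an exception for subjects who stop dosing.
- **Adverse events.** Protocol 8.1.4 states: "Adverse events will be captured from start of study drug treatment through Day 94". Protocol 8.1.1 and 8.1.2 give the same period, again without exception.

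On what triggers a stop, Protocol 6.9.2 says: "The study drug will be permanently discontinued for any subject who meets a DLT criterion". The Day 35 rule is not confined to dose-limiting toxicity; it covers any permanent stop.

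The SAP has two rules for a missing score. For clinical response, SAP 6.3 says: "A subject with a missing WOMAC pain score on the Study Knee at a visit will be considered to have failed". For the continuous analyses, SAP 4.4 leaves missing values missing, apart from item-level imputation within WOMAC subscales.

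**The concern.** Outcome assessment should not depend on whether a subject completed dosing. Here a subject can be willing to attend, still be on study, and have no scheduled measurement at Days 64 and 94. The gap would come from the protocol, not from the subject.

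WOMAC pain, stiffness, function and total at Days 64 and 94 are named secondary endpoints. SAP 6.2 tests 5% against 1% at those days, SAP 6.3 tabulates response and durability to Day 94, and Protocol 9.5.7 plans an interim analysis at Day 64. The two missing-data rules also treat the same stopper differently, as a failure in one analysis and as absent in the other.

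On safety, the scheduled Day 94 laboratory tests and vital signs would be missing for subjects who may have stopped because of toxicity. By Table 6-3 and Appendix C, their last scheduled laboratory tests would be at Day 35 and their last scheduled vital signs at Day 5.

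**Working it through.** **1. What a stopper contributes under each reading**

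| Item | Protocol 6.10 / SAP 3.2.4 followed | Protocol 3.1 / SAP 3.1 followed |
|---|---|---|
| Day 35 WOMAC pain (primary) | collected | collected |
| Day 64 and 94 WOMAC, VAS | not scheduled | collected |
| Day 94 laboratory tests, vital signs | not scheduled | collected |
| Adverse events to Day 94 | required (8.1.1, 8.1.2, 8.1.4) | required |
| Clinical response, Days 64 and 94 (SAP 6.3) | non-responder | as observed |
| 5% vs 1% ANCOVA, Days 64 and 94 (SAP 6.2, 4.4) | dropped | included |

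**2. Durable response**

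SAP 6.3 fails a subject who has less than a 50% reduction at two or more visits after Day 5. Take a stopper who responded at Days 5, 19 and 35 and has no later visits.

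- If the missing-means-failure rule carries over, Days 64 and 94 are two failures and the subject fails durability.
- If it does not, no observed visit is below 50%, and the subject could be classed as durable through Day 35.

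The missing-score sentence is written for clinical response at that visit. The SAP does not say whether it also governs durability.

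**3. Effect on a responder rate**

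Inputs: 40 per arm (SAP 9). The number of stoppers in an arm, k, and the share r of them who would have responded are assumptions; the documents give neither.

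- Understatement = (k/40) × r
- k = 0: 0 points
- k = 2, r = 50%: 0.05 × 0.50 = 2.5 points
- k = 4, r = 80%: 0.10 × 0.80 = 8 points
- k = 8, r = 80%: 0.20 × 0.80 = 16 points

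The highest responder rate the arm could show is (40 − k)/40: 95%, 90%, 85% and 80% for k = 2, 4, 6 and 8.

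**4. Effect on power of a Day 64 or 94 comparison**

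First, the plan's own figure (SAP 9: difference 63, SD 100, 40 per arm, two-sided 5%):

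- Standard error = 100 × √(2/40) = 22.36; 63/22.36 = 2.817
- Power = Φ(2.817 − 1.960) = Φ(0.857) = 80.4%, against the stated 80%. The noncentral t gives 79.5%.

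The SAP states no design difference for 5% versus 1% at Days 64 and 94, so the same inputs are borrowed for illustration, with k subjects lost from one arm. For k = 4:

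- Standard error = 100 × √(1/36 + 1/40) = 22.97; 63/22.97 = 2.74
- Power by noncentral t = 77.2%

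For k = 2, 6 and 8 it is 78.4%, 75.9% and 74.5%. The loss of precision is small. What matters more is which subjects are lost.

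**5. Is the loss likely to differ by arm?**

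In VZU00023 (Protocol 1.3), active against vehicle rates were 100% vs 35% for burning-stinging pain, 72% vs 15% for erythema, 56% vs 31% for pruritus and 20% vs 3.8% for coughing or sneezing. A dose-limiting toxicity forces a stop, and Protocol 4.2 does not allow replacement when the reason is lack of tolerability. These facts make an imbalance toward the capsaicin arms plausible. They do not measure it: the same study reported no discontinuations for adverse events in either arm.

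**The case against.** **The text does not say only to Day 35.** Protocol 6.10 keeps stoppers on study and does not list stopping drug as a reason for removal from the study. Day 35 could be meant as a minimum that secures the primary endpoint, with Section 3.1 governing the rest. That reading is open, but so is the other, and a site has no means of choosing. The need to reconcile stands.

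**Late safety follow-up is not lost.** A reader might infer that it is, but the documents do not support this. Adverse events are captured to Day 94, unresolved serious events are followed to outcome (8.1.4), and related Grade 3 or higher events during administration are followed until they resolve (6.9.3). Section 6.5 also allows vital signs and blood tests at early termination. What can be lost is narrower: the scheduled Day 94 laboratory tests and vital signs, and the Day 64 and 94 visits at which Table 6-3 places adverse event assessment.

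**There may be few or no stoppers.** VZU00021 and VZU00023 reported no discontinuations for adverse events, and related events reached Grade 2 at most. Application-site reactions have a Grade 3 threshold for dose-limiting toxicity in Protocol 3.2. This stands, and zero belongs in the range. The same section also counts other Grade 2 or higher events, so zero is not assured.

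**The affected analyses are secondary.** Response and durability are tabulated without a test. SAP 6.2 tests only 5% against 1% at Days 64 and 94; the protocol synopsis lists vehicle comparisons of stiffness, function and total at those days, but the SAP does not carry them. SAP 4.5 calls the study exploratory. This also stands. With 36 of 40 still in an arm, it would be too strong to say that the late ANCOVAs compare only those who tolerated the drug.

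**Scoring a subject who stopped for toxicity as a failure can be a defensible conservative choice.** It can, but SAP 6.3 does not present it as one. The score would arise because no visit was scheduled.

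**Conclusion.** The contradiction between Day 35 and Day 94 is in the text of both documents and needs reconciling. If sites follow Protocol 6.10, stoppers become non-responders at Days 64 and 94 under SAP 6.3 and disappear from the 5% versus 1% ANCOVAs at those days. Durable-response failure follows as well only if the missing-score rule is taken to cover durability, so it should not be said that every stopper fails durability automatically.

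The size is hypothetical. It is zero with no stoppers. It is 8 points on one arm's responder rate under the assumed 4 of 40 stopping with 80% of them true responders, and 2.5 to 16 points across the non-zero assumptions shown. A greater loss in the capsaicin arms is plausible but inferred.

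The Day 35 primary analysis is not affected. This is a low-cost improvement to the secondary and durability data, not a threat to the main result.

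**What to change.** In Protocol 6.10 and SAP 3.2.4, change Day 35 to Day 94 for the WOMAC, VAS, adverse event, laboratory and vital-sign assessments already in the schedule, and state that this applies whether or not all four doses were given. Both sections would then agree with Protocol 3.1, SAP 3.1 and Protocol 8.1. No dose, stopping rule or other treatment provision changes. The SAP 6.3 rule would then act only on visits that were scheduled and missed.

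The cost is up to two further visits, both already in the schedule of events, for each subject who stops. It also needs a SAP revision and a short protocol amendment, which under Protocol 10.4 requires investigator signature and IRB/IEC review before implementation.
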